**11.b: Criteria for Discontinuing or Modifying Intervention:**

- There will be modification in the trial if any harm occurs to the patient.
- If patients shows any signs of progression of the disease, increased recession or periodontal abscess.

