**PRF preparation:**

This procedure will be done only if the patient is allocated to group A where PRF will be placed and after the flap in the recession site has been prepared. Just before SCTG harvesting, blood will be taken from the anticubital region with a 24-gauge needle and injected into the 10-mL glass coated collection tube without anti-coagulant then immediately centrifuged at 2700 rpm for 12 minutes with a table centrifuge. The fibrin clot will be collected from the middle part of the tube and packed tightly in 2 sterile saline impregnated gauze in order to obtain a fibrin membrane.

A post-surgery protocol will be implemented emphasizing wound stability and infection control, including 0.12% chlorhexidine rinse twice per day. Gingival sutures will be removed 2 weeks post-surgery. Mechanical plaque control in the surgical area will be reinstated at week 8 following surgery. Patients will be recalled for supragingival scaling and oral hygiene instructions on a monthly basis for the 6-month observation interval.

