#### **11-d: Concomitant care**

The patients will receive postoperative instructions and oral hygiene guidelines that should be followed during the 6 month follow-up period. Patients will be recalled every 1 week for first month and then every month for supportive periodontal therapy till 6 months follow up.

Medications: Chlorohexidine 0.12% mouthwash 2 times/day for 1 week

Brofen 400 mg 3 times/day for 5 days

Soft tooth brush is to be used

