### 13. Participant timeline

- After accepting to be enrolled in this study, all patients will receive proper oral hygiene instructions and will be motivated to stick to these instructions.
- After receiving the treatment, patients will be followed-up for 6 months.

Time point	T0	T1	T2	T3(weekly till T4)	T4(1 month)	T5 (3 months)	T6(6 months)
Enrollment	X						
Eligibility screening	X						
Informed consent	X						
Initial phase (oral hygiene)		X					
Allocation			X				
Intervention			X				
Post-operative care				X	X		
		Assessment					
Radiograph	X			x	X	X	X
Recession depth		X				X	X
%of root coverage							X
Probing depth		X				X	X
Clinical attachment level		X				X	X
Gingival biotype		X				X	X
RES							X
Questionnaire					X		
Post-operative pain				X			

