**18-Data collection methods****18a-Data collection method:**

The phone numbers and address of the patient included in the study will be recorded from them or extracted from the patient's file which will be available at [name] office , the one responsible for filing system in the Oral Medicine and Periodontology department. The data will be collected by dr [name], whether personal or numerical. They will be stored on excel sheets as an electronic copy and printed hardcopy sheets. The outcome data will be collected at 0, 3 and 6 months. Numerical data will be presented as mean and standard deviation

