### **30-Ancillary and Post Trial Care**

All patients will be followed up for one year after the clinical trial is over.

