### 3. Root coverage esthetic score

The RES system evaluates five variables 6 months following surgery: gingival margin (GM), marginal tissue contour (MTC), soft tissue texture (STT), mucogingival junction (MGJ) alignment, and gingival color (GC). The clinical esthetic evaluation is performed without magnification. Zero, 3, or 6 points are used for the evaluation of the position of the gingival margin, whereas a score of 0 or 1 point is used for each of the other variables

- GM: -Zero points = failure of root coverage (gingival margin apical or equal to the baseline recession)
  - 3 points = partial root coverage;
  - 6 points = CRC.
- MTC: -Zero points = irregular gingival margin (does not follow the CEJ).
  - 1 point = proper marginal contour/ scalloped gingival margin (follows the CEJ).
- STT: - Zero points = scar formation and/or keloidlike appearance .
  - 1 point = absence of scar or keloid formation.
- MGJ: - Zero points = MGJ not aligned with the MGJ of adjacent teeth.
  - 1 point = MGJ aligned with the MGJ of adjacent teeth.
- GC: -Zero points = color of tissue varies from gingival color at adjacent teeth.
  - 1 point = normal color and integration with the adjacent soft tissues.

Thus, the ideal esthetic score is 10.

Zero points are assigned if the final position of the gingival margin is equal or apical to the previous recession depth (failure of root coverage procedure), irrespective of color, the presence of a scar, MTC, or MGJ. Zero points are also assigned when a partial or total loss of interproximal papilla (black triangle) occurred following the treatment.

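### Section 11.b makes a bad value of the primary outcome a reason to stop or change the intervention, without saying that measurement continues afterwards or which reading is analysed

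*Combined protocol and SAP*

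**What the plan says.** Section 11.b has two bullets. One reads "There will be modification in the trial if any harm occurs to the patient" and does not say what the modification is. The other reads "If patients shows any signs of progression of the disease, increased recession or periodontal abscess" and stops there, with no action attached. Sections 7 and 12 make recession depth the primary outcome, read at baseline, 3 months and 6 months.

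The general follow-up text has no exceptions:

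- Section 13: "After receiving the treatment, patients will be followed-up for 6 months".
- Section 18a: "The outcome data will be collected at 0, 3 and 6 months".
- The post-surgery text in Section 11a recalls patients "on a monthly basis for the 6-month observation interval", and Section 11-d, after weekly visits in the first month, "every month for supportive periodontal therapy till 6 months follow up".
- Section 30: "All patients will be followed up for one year after the clinical trial is over".
- The esthetic score in Appendix item 3, taken at 6 months, gives zero points for "failure of root coverage (gingival margin apical or equal to the baseline recession".

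Section 20 names a two-way repeated-measures ANOVA, with a t-test or Mann-Whitney test if time is not important. It gives no analysis set, no rule for missing values and no rule for readings taken after a change of treatment. Section 14 raises the number per arm from 14 to 17 to allow for losses.

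**The concern.** The intervention is a single operation. Once it is done, stopping could in practice only mean ending participation, and changing could only mean further treatment of the site. The plan does not say which is meant, or whether either is. Both would act on the 6-month reading, and both would be set off by that same outcome going badly.

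The two routes lead to the same place. If follow-up ends, the 6-month value is missing, and a standard repeated-measures ANOVA then also discards the patient's valid 3-month value. If the site is treated again and only the later reading is used, a failure of the assigned surgery is scored as whatever the second treatment achieved. Either way the arm with the failure looks better than it was. The benefit of PRF would be understated if that is the control arm and overstated if it is the PRF arm.

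The allowance in Section 14 replaces numbers, not failures. The telephone calls, possible home visit and transport fees in Sections 11-c and 18b deal with missed visits, not with what follows an 11.b event. Section 17 leaves operator and participants unblinded, so undefined criteria could also be applied differently in the two arms.

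**Working it through.** **Inputs from Section 14.** Difference 0.45 mm; 0.38 mm taken as the SD; 80% power; two-sided 5% (sidedness from Section 20); 12, then 14, then 17 per arm.

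**The plan's own figure.** n = 2 × (1.960 + 0.842)² × 0.38² / 0.45² = 11.2, so 12 per arm, which reproduces. The later steps are consistent with 12/0.864 = 13.9, so 14, and with 14/0.85 = 16.5, so 17. The plan states neither factor. The allowance amounts to 3/17 = 17.6% losses.

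**Shift from one affected patient.** Let one patient's reduction in recession lie a distance *gap* below the mean of the other 16 in the arm. The mean of all 17 is then the others' mean minus gap/17. Losing that patient, or re-treating the site up to the others' mean, raises the arm mean by gap/17. The standard error of the difference is 0.38 × √(2/17) = 0.130 mm.

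| Assumed gap | Shift = gap/17 | Share of 0.45 mm | In standard errors |
|---|---|---|---|
| 1 mm | 0.06 mm | 13% | 0.45 |
| 2 mm | 0.12 mm | 26% | 0.90 |
| 3 mm | 0.18 mm | 39% | 1.35 |

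The gaps are assumptions. Section 11.b does not say what an increase is measured against. If it means worse than baseline, the gap exceeds the mean reduction among the others, which the plan does not give. If it means worse than an earlier postoperative visit, the gap may be smaller.

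**When the exposure arises.** Recession depth is scheduled only at baseline, 3 and 6 months.

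- Event first seen at month 6: the reading is already taken and nothing is lost.
- Event seen at month 3 and acted on: the 3-month reading exists, but month 6 may be missing or altered.
- Event seen at a weekly or monthly recall and acted on: there may be no scheduled reading before the action.

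So the exposure lies mainly in events acted on before the month-6 reading.

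**What a better model can recover.** Suppose the failure is seen at month 3, persists at month 6 and is not measured then. With equal SDs at both visits, a likelihood model using the 3-month value leaves a bias of about (1 − ρ) × gap/17, where ρ is the correlation between the two visits. For a 2 mm gap this is 0.06, 0.035 or 0.01 mm at assumed ρ of 0.5, 0.7 or 0.9, against 0.12 mm if the patient is dropped. The model reduces the bias but does not remove it, and it cannot help a patient lost before month 3. Continued measurement is the main protection.

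**The case against.** The strongest reply is that the harm depends on events the plan never describes. No section mentions withdrawal or second treatment of the site. The general text points to measuring everyone to 6 months, and a 6-month score for a margin at or beyond its baseline position suggests that failures are expected to be present and assessed. This stands. A reader might infer that the plan removes or re-treats failing patients and that the comparison is therefore biased; the documents do not support that. What remains is that 11.b is the section on exceptions, its action is undefined, and no general statement refers to it. The extra year in Section 30 begins after the trial and supplies no trial outcome. Full attendance would also not settle which reading counts at a site that had been treated again.

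It can also be said that the missing analysis set and missing-data rule are general gaps, affecting any dropout. That is true, but here the loss would be tied to the outcome, which is where the gap does most damage.

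A last point concerns cost. A reader might infer that keeping failures in the analysis would wreck the trial's power. In a simulation with 17 per arm, SD 0.38 mm and the other patients differing by 0.45 mm, one failure kept in the PRF arm gives t-test power of about 78%, 43% and 11% for gaps of 1, 2 and 3 mm, against 92% with none. The Mann-Whitney test, which Section 20 names for non-normal data in the two-group comparison, gives about 80%, 78% and 78%. At the larger gaps most of the fall belongs to the t-test meeting one extreme value. It is not a reason to leave failures out.

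**Conclusion.** The point holds as an unclosed gap, not as a demonstrated bias. An adverse value of the primary outcome is a stated reason to stop or change the intervention, and the plan does not say that scheduled measurement continues or which reading is analysed. The named ANOVA, in its standard form, would drop a patient without a 6-month value. If 11.b is acted on by loss or re-treatment before month 6, each such patient moves the result in favour of that patient's own arm, by 0.06 to 0.18 mm under the assumed gaps. The number of such events cannot be estimated from the documents, and equal losses in both arms would largely cancel in the difference. It should be settled before any outcome is seen, because a choice made after failures are known would be open to the result. Confidence is medium, because the general text may already reflect an intention to measure everyone.

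**What to change.** Leave the clinical criteria and their consequences to the sponsor.

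- **Section 11.b:** state that every randomised patient is still measured at 3 and 6 months whatever happens under this section, and that recession depth is recorded before any further treatment of the site.
- **Section 20:** analyse all randomised patients as assigned, using a likelihood-based repeated-measures model on the 3- and 6-month values, adjusted for baseline recession depth, with the 6-month difference as the primary contrast.
- **Re-treated sites:** state the handling in advance and report both the reading before re-treatment and the observed 6-month value. Which is primary is the sponsor's choice. The first isolates the assigned surgery but assumes no later change; the second reflects whatever care was given.

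The cost is a few sentences and one extra probe reading per event; baseline recession is already collected. Keeping a failure may also raise the SD of that arm: √((15 × 0.38² + gap² × 16/17)/16) = 0.44, 0.61 or 0.82 mm for gaps of 1, 2 or 3 mm. This holds if the planned 0.38 mm excludes failures, which Section 14 does not say.

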**11-c: Strategies to improve adherence to intervention:**

The patient will be followed up weekly the first month. The operator should explain the importance of follow up. Adherence to oral hygiene measures will be verified by showing the patient the amount of plaque on the periodontal probe and bleeding on probing using a mirror. The patient will receive 2 phone calls to remind him the follow up visit. Phone

number of a close person will be collected in case we cannot reach him on his phone. If the patient does not show up a home visit might be considered.

#### **11-d: Concomitant care**

The patients will receive postoperative instructions and oral hygiene guidelines that should be followed during the 6 month follow-up period. Patients will be recalled every 1 week for first month and then every month for supportive periodontal therapy till 6 months follow up.

Medications: Chlorohexidine 0.12% mouthwash 2 times/day for 1 week

Brofen 400 mg 3 times/day for 5 days

Soft tooth brush is to be used

#### **12- Outcomes:**

[name] is responsible for measuring all the outcomes and collecting data.

	Outcome name	Measuring Device	Measuring Unit
Primary1ry	Recession depth	William's graduated Periodontal probe	Mm
Secondry2ry	Recession width	William's graduated Periodontal probe	Mm
	Root coverage gain	William's graduated Periodontal probe	Mm
	Probing depth	William's graduated Periodontal probe	Mm
	Clinical attachment level	William's graduated Periodontal probe	Mm
	Gingival biotype	William's graduated Periodontal probe	Mm
	Width of keratinized gingiva	William's graduated Periodontal probe	Mm
	Patient satisfaction	Printed questionnaire Binary (Zuhr et al.2014)	Yes/No
	Root coverage	Score	Categorical

	esthetic score	(Cairo et al. 2009)	
	Post-Operative Pain	Numerical Rating Scale (NRS) (Breivik et al. 2008)	Numerical

The probe is held parallel to the long axis of the tooth. The pressure applied with the probe tip should be between 10-20 grams. Blanching of the gingiva should be avoided.

- Recession depth: from the CEJ to the margin of the gingiva at the midbuccal point of the teeth.
- Recession width: measured horizontally between two borders of the recession
- % of root coverage: (preoperative vertical recession – postoperative vertical recession/preoperative vertical recession) x 100.
- Probing depth: measured from the gingival margin to the base of the pocket probe at the midbuccal point of the teeth.
- Clinical attachment loss: measured from the CEJ to the base of the sulcus at the midbuccal point of the teeth.
- Gingival biotype: under local anesthesia from 3 mm below the gingival margin trans-gingivally piercing tissues horizontally, perpendicular to the long axis of the tooth until it contacts bone.
- Width of keratinized gingiva: from the margin of the gingiva to the mucogingival junction at the midbuccal point of the teeth.
- Patient satisfaction: printed yes/ no questionnaire with 3 questions
- Root coverage esthetic score **(Cairo et al. 2009)**
- Post-Operative Pain: Numerical Rating Scale (NRS) with numbers from 0 to 10 ('no pain' to 'worst pain imaginable') for the first 2 weeks postoperatively. (Breivik et al. 2008)

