**- Rationale for carrying out the trial:**

Subepithelial connective tissue graft (SCTG) secured by a coronally advanced flap (CAF) is one of the substantial surgical alternatives and is utilized as often as possible because of its great consistency (**Wennstrom and Zucchelli, 1996; Paolantonio et al., 2002; Tozum and Demiralp, 2003**). However, uncertain complete root coverage (between 18.1 %and 86.7%) has been documented as well as confined regeneration of the lost attachment apparatus with a remedial through long junctional epithelium or adaptation of connective tissue to the root surface after the use of CAF+SCTG (**Cummings et al. 2005**).

One of the enhancers of periodontal tissue regeneration and promoters of early wound healing is found to be the Platelet rich fibrin (PRF) (**Tozüm et al. 2003**). There are only a few reports documenting the use of platelet rich plasma (PRP) in aesthetic periodontal surgery. **Petrungaro (2001)** published a case series in which PRP, SCTG and collagen membranes were used to cover gingival defect. The 2 months study resulted

in 3 mm root coverage. Accordingly, this study will assess the effect of PRF as an adjunct to CAF+SCTG on root coverage outcomes.

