**7. Objectives of the study:**

This research will be conducted in an attempt to achieve complete root coverage with physiologic probing depth and a harmonious view with the adjacent tissues using PRF in conjunction with CAF and SCTG.

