 **Research hypothesis:**

Null hypothesis: In patients with Miller class I and II gingival recession, there is no difference in root coverage outcomes following placement of PRF in conjunction with CAF and SCTG compared to CAF and SCTG alone.

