 **The secondary objectives:**

	Outcome name	Measuring Device	Measuring Unit
Primary1ry	Recession depth	William's graduated Periodontal probe	mm
Secondary2ry	Recession width	William's graduated Periodontal probe	mm
	Root coverage gain	William's graduated Periodontal probe	mm
	Probing depth	William's graduated Periodontal probe	mm

		probe	
Clinical attachment level	William's graduated Periodontal probe	mm	
Gingival biotype	William's graduated Periodontal probe	mm	
Width of keratinized gingiva	William's graduated Periodontal probe	mm	
Patient satisfaction	Printed questionnaire Binary ( Zuhr et al.2014 )	Yes/No	
Root coverage esthetic score	Score (Cairo et al. 2009)	Categorical	
Post-Operative Pain	Numerical Rating Scale (NRS) (Breivik et al. 2008)	Numerical	

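### Do the missing bracket in the root coverage formula, its mismatched label and unit, and the unlisted complete-coverage outcome call for a change to the plan?

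*Combined protocol and SAP*

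**What the plan says.** Three parts of the combined protocol and SAP bear on this.

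- **Formula.** Section 12 (Outcomes) gives the only definition of percentage coverage: "of root coverage: (preoperative vertical recession – postoperative vertical recession/preoperative vertical recession) x 100". Its inputs are the recession depths before and after surgery, defined in the same list: "Recession depth: from the CEJ to the margin of the gingiva at the midbuccal point of the teeth".
- **Name and unit.** The outcome table under the secondary objectives and the one in section 12 both list "Root coverage gain", measured with a periodontal probe in mm. The definitions in section 12 have no such entry and give the percentage instead. The section 13 timeline also schedules only the percentage "of root coverage", at 6 months.
- **Complete coverage.** Section 7 says: "This research will be conducted in an attempt to achieve complete root coverage with physiologic probing depth". The null hypothesis is that "there is no difference in root coverage outcomes following placement of PRF". The rationale notes that "uncertain complete root coverage (between 18.1 %and 86.7%) has been documented" for the comparator procedure. Complete coverage has no row in either outcome table, in the definitions or in the timeline. It is named as an assessed item only in Appendix 3, as the 6-point level of the gingival margin component of the esthetic score.

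The PICOTS outcome, the research question, the primary objective and the sample size in section 14 all specify recession depth.

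**The concern.** The hypothesis is framed on root coverage, so a reader expects one definition, one name and one unit for it. On a strict reading the formula is wrong, and badly so: a 3 mm recession that does not improve scores 200%, the same as a 2 mm recession that is fully covered. The tables then give what may be the same measure a different name and a unit that does not fit a percentage.

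Complete coverage is the goal in section 7, and its inconsistency is part of the reason for doing the trial, yet it is not listed. With two possible sources, recession depth and the esthetic score, the choice might be made after the data are seen. The total esthetic score cannot settle it, because some totals are compatible with both partial and complete coverage, and the appendix adds that "Zero points are also assigned when a partial or total loss of interproximal papilla (black triangle) occurred following the treatment".

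At stake would be a wrong secondary result, or one chosen after the fact.

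**Working it through.** **1. The plan's own figure.** Section 14 uses a difference of 0.45 mm, an SD of 0.38 mm, 80% power and a 5% level; section 20 makes the tests two-tailed. By the normal approximation, n = 2 × (1.960 + 0.842)² × (0.38/0.45)² = 11.2, rounded up to 12 per group. This agrees with the plan. (The t-based value is 12.2, with power 79.2% at 12.) The calculation is on the decrease in recession depth, so nothing below affects it.

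**2. The formula.** Let p and q be the recession depths in mm before and after surgery.

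- Strict reading: 100 × (p − q/p)
- Intended: 100 × (p − q)/p
- Difference: strict − intended = 100 × (p − 1)

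| p to q (illustrative, mm) | Strict | Intended |
|---|---|---|
| 3 to 0 | 300% | 100% |
| 3 to 1 | 266.7% | 66.7% |
| 3 to 3 | 200% | 0% |
| 2 to 0 | 200% | 100% |
| 2 to 1 | 150% | 50% |
| 4 to 1 | 375% | 75% |

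For q between 0 and p, the strict value runs from 100(p − 1) to 100p. Once baseline recession is 2 mm or more, any improvement at all therefore prints above 100%. A single shallow defect could give a plausible number, but a column of results could not. The strict reading also subtracts a ratio without units from a length in mm. Only one sensible reading is left.

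**3. The label and unit.** There are two possibilities.

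- *One outcome.* The tables carry the wrong name and unit for the percentage, which section 12 defines.
- *Two outcomes.* The mm gain is p − q, and the percentage is that gain divided by p.

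Both need only p and q. Section 13 schedules recession depth before surgery and at 3 and 6 months, so either quantity can be computed under either reading. The mm gain is simply the decrease in the primary measure, so it is not a separate source of evidence.

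**4. Complete coverage.** Recession depth is measured from the cemento-enamel junction, so complete coverage at 6 months is a depth of 0, or equivalently 100% coverage. The gingival margin component is scored separately as 0, 3 or 6. The other four components score 0 or 1 each, so partial coverage totals 3 to 7 and complete coverage totals 6 to 10. Totals of 6 and 7 are ambiguous, but nobody needs the total: the depth and the separate component each give the answer.

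**5. What a formal comparison would yield.** The 50%, the 80% and the 30-point difference are assumptions; 18.1% is the low end of the range in the rationale. Power is for the exact two-sided Fisher test at 0.05. The 95% CI half-width is 1.96 × √{[p₁(1 − p₁) + p₂(1 − p₂)]/n}, where p₁ and p₂ are the proportions with complete coverage.

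| Complete coverage | n per group | Power | CI half-width |
|---|---|---|---|
| 50% v 80% | 14 | 0.260 | 33.5 points |
| 50% v 80% | 17 | 0.319 | 30.4 points |
| 18.1% v 48.1% | 14 | 0.270 | 33.0 points |
| 18.1% v 48.1% | 17 | 0.325 | 30.0 points |

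For the first row: 1.96 × √[(0.25 + 0.16)/14] = 0.335. Even a 30-point difference would usually be missed, and its interval would reach about zero.

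**The case for a change.** The strongest case for a change is that the repair is nearly free. It takes one bracket, one label and unit in two tables, and one outcome row with its analysis line, with no new data. The mismatch of name and unit is real on either reading: if one outcome is meant, the tables mislabel it; if two, the mm gain has no definition and the percentage is missing from the tables. The mismatch is consistent across both tables, so loss of layout in the text does not explain it. Naming complete coverage in advance, with its source, would also remove a choice that could otherwise be made late.

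The clerical part of this stands: the text is untidy, and anyone editing it would put it right. The statistical part does not. No realistic path leads from the missing bracket to a published wrong number, and the label does not alter what is measured. If the typeset page shows a stacked fraction, the bracket point disappears altogether.

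On complete coverage, section 7 states a treatment goal and does not define an endpoint. The reference to root coverage outcomes in the null hypothesis is generic, and every statement that fixes the outcome names recession depth. The remaining freedom is small, since a depth of 0 and a gingival margin component of 6 describe the same state. A further binary test would join nine listed secondary outcomes with little chance of informing anyone.

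**Conclusion.** The observations are accurate, but they do not call for a change to the plan. The missing bracket and the differing label are clerical slips that an analyst will resolve without hesitation. The strict formula overstates coverage by 100 × (p − 1) percentage points, for example 200 points at a 3 mm baseline, and so gives itself away. Complete coverage is unlisted but not lost: it follows from recession depth at 6 months and can be described as counts and percentages. Adding it as a tested outcome would be a preference and would not repair an error, with power of about 0.26 to 0.33 for an assumed 30-point difference.

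The primary outcome, the sample size and the trial's main conclusion are unaffected. This rests on two assumptions: that recession depth is recorded at baseline and at 6 months as section 13 schedules, and that the results are reported with the unit stated.
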